- Possible further escalation from the previous step by 1 or more steps, according to clinical judgment and under the same recommendation as above.
- Maximum escalation to 1.5 mg/kg qd for 3 weeks.

If, after a minimum of 3 weeks of oral prednisone at 1.5 mg/kg qd, DC is not attained, then the participant will be considered a treatment failure.

For participants achieving DC with a daily prednisone dose of 0.5 mg/kg, prednisone will be maintained at 0.5 mg/kg qd until CR and 2 weeks thereafter, or until end of consolidation (EoC, defined as the time at which no new lesions have developed for a minimum of 2 weeks and approximately 80% of lesions have healed) and 4 weeks thereafter, after which tapering will be initiated. For participants achieving DC with an escalated prednisone dose (ie, >0.5 mg/kg qd), the prednisone dose will be maintained until 2 weeks after achieving DC, then tapering will be performed according to the following stepwise procedure: dose reductions by 0.25 mg/kg qd (according to [Table 3](#)) every 2 weeks until the starting dose is reached (ie, 0.5 mg/kg qd). Then the starting dose (0.5 mg/kg qd) will be maintained until a sustained CR is achieved for 2 weeks, after which further tapering will be initiated, or prednisone tapering below 0.5 mg/kg qd may be initiated in case of sustained EoC for at least 4 weeks. Further tapering will be performed thereafter, as long as CR or EoC are sustained. The rules for tapering are shown in [Table 3](#). Each new tapered prednisone dose until 20 mg/day must be maintained for 2 weeks. Then, the prednisone dose is further tapered by 2.5 mg/day per week. When 10 mg/day is reached, this dose level will be maintained until CRmin has been achieved. Prednisone can then be further tapered upon clinical judgment by the investigator.

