^{ee} The GTI assessment will be performed only at baseline, W15 and EoS/ED. If W15 does not coincide with an on-site visit, then the assessment should be performed at the next on-site visit.

^{ff} Participants will be trained to self-administer IMP (foreseen in the OLE trial; not in the ARGX-113-1904 trial) during the first 4 visits as of V3 when IMP is administered; thereafter, training for self-administration is optional (only if needed).

^{gg} IMP will be administered until CRmin. To ensure proper safety monitoring, participants should remain at the site for at least 1 hour after the first administration and for 15 minutes after subsequent administrations. Participants will be released according to their clinical status. For Germany-specific monitoring instructions, refer to Section 10.16.2.1. Participants who experience treatment failure, or flare after achieving CRmin, will be allowed to roll over into the OLE trial ARGX-113-1905 earlier than W31. Participants who do not roll over into trial ARGX-113-1905 will complete the treatment-free follow-up period.

^{hh} Disease assessment parameters include disease control (DC), end of consolidation (EoC), complete clinical remission (CR), complete remission on minimal therapy (CRmin), complete remission off therapy (CRoff), flare, and treatment failure. Participants who have achieved CR and have new lesions should come to the clinic for a UNS for disease assessment.

ⁱⁱ Prednisone dose tapering will begin 2 weeks after achieving CR or 4 weeks after sustained EoC (thus, no new lesions have developed for a minimum of 6 weeks and approximately 80% or more of lesions have healed).

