Treatment failure: Prednisone dose escalation in the trial will happen in a stepwise approach (from 0.5 to 0.75, 1, 1.25 and 1.5 mg/kg per day), investigators being able to increase the dose by 1 or more steps according to the severity of the disease progression. The prednisone dose of 1.5 mg/kg per day for 3 weeks without DC defines treatment failure, in accordance with the guidelines.²⁴ In such circumstances, participants will be considered as nonresponders and will be invited to roll over prematurely into the OLE (trial ARGX-113-1905). Additionally, flare between DC and CRmin that is not controlled by a prednisone dose that is 2 dose levels above the dose at which the flare is observed and that is of at least 0.3 mg/kg qd (refer to Table 3) or the occurrence of an SAE considered related to prednisone by the investigator will be defined as treatment failure.

Prednisone tapering: Two weeks after DC is achieved after an escalated prednisone dose above 0.5 mg/kg qd, prednisone tapering will begin (Section 6.8.1). Prednisone tapering is a procedure that is applied by all practitioners, in order to minimize the side effects of corticosteroids while preventing a flare of the disease. In this trial:

- Two-week intervals between tapering are defined with a step down of 0.25 mg/kg from 1.5 to 0.5 mg/kg per day (eg, from 1.5 to 1.25 mg/kg per day, then to 1 mg/kg and 0.75 mg/kg per day; refer to Table 3). The dosage of prednisone at which CR is achieved (which cannot be lower than the starting dose 0.5 mg/kg per day) will be maintained for 2 weeks after CR for observing a sustained CR, or prednisone tapering may be initiated or continued in case of sustained EoC (defined by the time at which no new lesions have developed for a minimum of 2 weeks and approximately 80% of lesions have healed) for at least 4 weeks.
- When CR is observed on daily prednisone of no lower than 0.5 mg/kg for 2 weeks, or when sustained EoC is observed, tapering may be initiated (see Section 6.8.1). Each new tapered prednisone dose until 20 mg/day must be maintained for 2 weeks. Then,

the prednisone dose is further tapered by 2.5 mg/day per week. When 10 mg/day is reached, this dose level will be maintained until CRmin has been achieved.

- When CRmin is achieved, prednisone can be tapered further upon clinical judgment, with the recommendation of a prednisone decrease by 2.5 mg/day every 4 weeks.

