6.8.1. Concomitant Pemphigus Therapy

All participants, regardless of treatment assignment, will concomitantly receive oral prednisone (or equivalent such as prednisolone) at 0.5 mg/kg qd as a starting dose. Except for oral prednisone (or equivalent), no other systemic therapies (eg, immunosuppressants, IVIg, immunoadsorption, anti-CD20 biologics) will be permitted during the trial.

At any post-baseline visit before DC is achieved, the prednisone dose will be adjusted by incrementing dosage according to clinical judgment, with the recommendation to increase by 1 or more steps (refer to [Table 3](#)) in case of disease progression or insufficient clinical change. To facilitate common judgments among investigators, recommendations for assessment of disease progression and insufficient clinical change are:

- Disease progression: increase of at least 5 in PDAI activity score compared to baseline score, observed at any post-baseline visit before DC.

- Insufficient clinical change: absence of DC after 3 to 4 weeks of the participant being treated at the starting baseline prednisone (or equivalent) dose or after 3 to 4 weeks of any new incremented dose of prednisone.

The recommendations of the prednisone dose escalation are:

- Stepwise escalation of daily prednisone dose by 1 or more steps according to clinical judgment in case of disease progression.
- Adjustment by incrementing dosage by 1 step according to clinical judgment in case of insufficient clinical change.
- Possible further escalation from the previous step by 1 or more steps, according to clinical judgment and under the same recommendation as above.
- Maximum escalation to 1.5 mg/kg qd for 3 weeks.

If, after a minimum of 3 weeks of oral prednisone at 1.5 mg/kg qd, DC is not attained, then the participant will be considered a treatment failure.

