For participants achieving DC with a daily prednisone dose of 0.5 mg/kg, prednisone will be maintained at 0.5 mg/kg qd until CR and 2 weeks thereafter, or until EoC (defined as the time at which no new lesions have developed for a minimum of 2 weeks and approximately 80% of lesions have healed) and 4 weeks thereafter, after which tapering will be initiated. For participants achieving DC with an escalated prednisone dose (ie, >0.5 mg/kg qd), the prednisone dose will be maintained until 2 weeks after achieving DC, then tapering will be performed according to the following stepwise procedure: dose reductions by 0.25 mg/kg qd (according to [Table 3](#)) every 2 weeks until the starting dose is reached (ie, 0.5 mg/kg qd). Then the starting dose (0.5 mg/kg qd) will be maintained until a sustained CR is achieved for 2 weeks, after which further tapering will be initiated, or prednisone tapering below 0.5 mg/kg qd may be initiated in case of sustained EoC for at least 4 weeks. Further tapering will be performed thereafter, as long as CR or EoC are sustained. The rules for tapering are shown in [Table 3](#). Each new tapered prednisone dose until 20 mg/day must be maintained for 2 weeks. Then, the prednisone dose is further tapered by 2.5 mg/day per week. When 10 mg/day is reached, this dose level will be maintained until CRmin has been achieved. Prednisone can then be further tapered upon clinical judgment by the investigator.

In case of flare in the period between DC and CRmin, the prednisone dose will be increased. A flare is defined by the appearance of 3 or more new lesions in a 4-week period that do not heal spontaneously within 1 week, or by the extension of established lesions in a participant who had achieved DC. If the flare occurs after CR and IMP was administered at home by a nurse, the participant will resume weekly on-site visits until he/she achieves CR again. Participants who are not controlled by a prednisone dose that is 2 dose levels above the dose at which the flare between DC and CRmin is observed and that is at least 0.3 mg/kg/day (according to [Table 3](#)) will be considered treatment failures. At visits when at least 1 new lesion is observed or established lesions remain extensive without being defined as a flare, the prednisone dose will be maintained or may be increased, according to clinical judgment. If the lesion resolves, tapering of the prednisone dose will be pursued as planned.

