The investigator should not implement any deviation from the concomitant oral prednisone (or equivalent) regimen, except for immediate safety concerns of the participants. After taking

appropriate action to ensure the safety of the participants, such concerns should be documented and communicated to the CRO's medical monitor and the sponsor.

Additionally, the following treatments may be used during the trial:

- Skin-directed topical corticosteroids
- Skin-directed topical antibiotics, antiseptics and moisturizers
- Buccal and mucosa-directed corticosteroids, antiseptics and anesthetics
- Analgesics
- Usual supportive treatments associated with intake of oral corticosteroids (eg, vitamin D, calcium, KCl, bisphosphonates) are intended to be used according to standard of care and current guidelines
- Non-live/non-attenuated vaccinations, and seasonal vaccinations (eg, influenza)

Table 3: Concomitant Prednisone Equivalent Doses (in mg) by Body Weight

Daily Prednisone Dose	Participant Body Weight (± 2.5 kg) ^a											Tapering Frequency	
	50 kg (47.5 – 52.4)	55 kg (52.5 – 57.4)	60 kg (57.5 – 62.4)	65 kg (62.5 – 67.4)	70 kg (67.5 – 72.4)	75 kg (72.5 – 77.4)	80 kg (77.5 – 82.4)	85 kg (82.5 – 87.4)	90 kg (87.5 – 92.4)	95 kg (92.5 – 97.4)	100 kg (97.5 – 102.5)		
1.5 mg/kg	75 mg	80 mg	90 mg	95 mg	105 mg	110 mg	120 mg	125 mg	135 mg	140 mg	150 mg	Tapering every 2 weeks	
1.25 mg/kg	60 mg	70 mg	75 mg	80 mg	85 mg	95 mg	100 mg	105 mg	110 mg	120 mg	125 mg		
1 mg/kg	50 mg	55 mg	60 mg	65 mg	70 mg	75 mg	80 mg	85 mg	90 mg	95 mg	100 mg		
0.75 mg/kg	35 mg	40 mg	45 mg	50 mg	50 mg	55 mg	60 mg	65 mg	65 mg	70 mg	75 mg		
0.5 mg/kg	25 mg	25 mg	30 mg	30 mg	35 mg	35 mg	40 mg	40 mg	45 mg	45 mg	50 mg		
0.3 mg/kg or 20 mg	20 mg	20 mg	20 mg	20 mg	20 mg	20 mg	25 mg	25 mg	25 mg	30 mg	30 mg		
0.2 mg/kg or 20 mg	Skip	Skip	Skip	Skip	Skip	Skip	20 mg	20 mg	20 mg	20 mg	20 mg		
Below 20 mg/day													
17.5 mg/day	17.5 mg	17.5 mg	17.5 mg	17.5 mg	17.5 mg	17.5 mg	17.5 mg	17.5 mg	17.5 mg	17.5 mg	17.5 mg		Tapering every week
15 mg/day	15 mg	15 mg	15 mg	15 mg	15 mg	15 mg	15 mg	15 mg	15 mg	15 mg	15 mg		
12.5 mg/day	12.5 mg	12.5 mg	12.5 mg	12.5 mg	12.5 mg	12.5 mg	12.5 mg	12.5 mg	12.5 mg	12.5 mg	12.5 mg		
10 mg/day	10 mg	10 mg	10 mg	10 mg	10 mg	10 mg	10 mg	10 mg	10 mg	10 mg	10 mg		

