8. TRIAL ASSESSMENTS AND PROCEDURES

Trial procedures and their timing are summarized in the SoA (refer to Section 1.3). Adherence to the trial requirements, including those specified in the SoA, is essential and required for trial conduct.

When a protocol-required procedure cannot be performed, the investigator will document the reason, and any corrective and preventive actions that he/she has taken to ensure that the normal processes are adhered to in source documents. The trial team should be informed of these incidents in a timely manner. This will be considered a protocol deviation and will be recorded accordingly.

Screening

At screening, all eligibility assessments should be performed after obtaining informed consent. All screening evaluations must be completed and reviewed before enrollment to confirm that potential participants meet all eligibility criteria. The investigator will maintain a screening log to record details of all participants screened and to confirm eligibility or record reasons for screening failure, as applicable.

The first day of the screening period is the day of the screening visit (the date of first screening visit is defined by the date of first screening procedure after signing the ICF).

Treatment Period

Each participant should attend each trial visit on the designated days. There is a permissible visit window of ± 2 days during the treatment period.

From signing of the ICF until the last trial-related activity, all AEs that occur and all concomitant medications that are taken and procedures performed, whether allowed or not, during the trial are to be recorded on the appropriate screens in the eCRF.

Immediate safety concerns should be discussed first with the CRO's medical monitor/sponsor's designee and then with the sponsor immediately upon occurrence or awareness to determine if the participant should continue or discontinue IMP. Additionally, an independent unblinded DSMB may review all unblinded safety data on a regular basis as specified in Section 10.1.5.

A minimum of 6 on-site visits, V1(BL)/W1 to W6, is required before switching to home administrations, even if CR is achieved earlier than W6. Home visits are allowed once participants achieve CR, but not before the W7 visit. The investigator should call the participant at least every 2 weeks until CRmin is achieved to confirm the participant is still in CR. On-site visits may continue at the investigator's discretion.

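### The Schedule of Activities footnote on prednisone tapering gives the wrong start for participants who reach disease control on more than 0.5 mg/kg

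*Protocol*

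**What the plan says.** The footnote is attached to the prednisone taper row of the Schedule of Activities (SoA) in Protocol 1.3: "Prednisone dose tapering will begin 2 weeks after achieving CR or 4 weeks after sustained EoC". It explains the second trigger as meaning that "no new lesions have developed for a minimum of 6 weeks and approximately 80% or more of lesions have healed". It names no dose and does not point to Section 6.8.1. The same sentence is footnote ii of Table 10 (COVID-19 schedule) and footnote dd of Tables 16 and 18 (China). The SAP's copy of the schedule in Section 9.5 also carries it.

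Section 6.8.1 sets out two paths:

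- **DC at 0.5 mg/kg:** hold that dose until 2 weeks after complete remission (CR) or 4 weeks after end of consolidation (EoC), then taper.
- **DC above 0.5 mg/kg:** "the prednisone dose will be maintained until 2 weeks after achieving DC, then tapering will be performed", in steps of 0.25 mg/kg every 2 weeks down to 0.5 mg/kg. The CR or EoC condition applies only to going below 0.5 mg/kg.

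The Synopsis and Section 4.1 state the same two paths. Section 4.2 says: "Two weeks after DC is achieved after an escalated prednisone dose above 0.5 mg/kg qd, prednisone tapering will begin". Section 4.2 is looser elsewhere. It also says that the dose at which CR is reached is kept for 2 weeks after CR, and that at sustained EoC a taper may start or continue.

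**The concern.** DC is the start of healing and CR is its completion. A taper that waits for CR or sustained EoC therefore starts later than one that waits for DC + 2 weeks, unless CR comes together with DC. A site that worked from the visit schedule would keep an escalated participant on the higher dose for longer than the protocol intends.

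Three things depend on that timing:

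- **Steroid exposure**, which the trial aims to reduce.
- **Normalised cumulative prednisone dose (NCPD)**, an alpha-controlled key secondary endpoint that counts doses actually taken (SAP 4.1.2.2).
- **The earliest possible CRmin**, which counts as a primary response only up to day 218 (SAP 4.1.2.1).

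**Working it through.** **1. The rules side by side**

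| Situation | SoA footnote | Synopsis, 4.1, 6.8.1 | Agree? |
|---|---|---|---|
| DC at 0.5 mg/kg | CR + 2 wk, or sustained EoC + 4 wk | CR + 2 wk, or EoC + 4 wk | Yes |
| DC above 0.5 mg/kg, taper down to 0.5 | the same, no exception made | DC + 2 wk | **No** |
| Taper below 0.5 mg/kg | the same | the same | Yes |

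The conflict is confined to the middle row.

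**2. Size of the difference**

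The plan states no figure to reproduce. The documents give no DC or CR times, so those below are assumed. Doses and steps come from Table 3.

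Let *T* be the footnote's trigger in weeks and *k* the number of 0.25 mg/kg steps above 0.5 mg/kg. At its earliest, the EoC route needs 6 weeks without new lesions. If that clock starts at DC, then *T* = min(CR + 2, DC + 6).

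- Extra time at the escalated dose = *T* − (DC + 2) = min(CR − DC, 4).
- Under 6.8.1 the participant leaves 0.5 mg/kg at max(*T*, DC + 2 + 2*k*). Under the footnote it is *T* + 2*k*.
- Delay in earliest CRmin = the difference = min(2*k*, CR − DC, 4).

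With CR at least 2 weeks after DC, both quantities lie between 2 and 4 weeks. At 0.75 mg/kg (*k* = 1) the CRmin delay is 2 weeks, while the extra hold is still 2–4 weeks.

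**3. Example: 60 kg, 0.75 mg/kg from week 3, DC week 5, CR week 9, no flare**

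*T* = min(11, 11) = week 11. Elapsed week *w* is day 7*w* + 1.

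| Dose | 6.8.1: days, mg | Footnote: days, mg |
|---|---|---|
| 30 mg | 21, 630 | 21, 630 |
| 45 mg | 28, 1,260 | 56, 2,520 |
| 30 mg | 28, 840 | 14, 420 |
| 20 mg | 14, 280 | 14, 280 |
| 17.5, 15, 12.5 mg | 21, 315 | 21, 315 |
| 10 mg to day 218 | 106, 1,060 | 92, 920 |
| **Total** | **218, 4,385** | **218, 5,085** |

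- The 10 mg dose is reached at week 16 versus week 18. Eight weeks later CRmin falls at week 24 (day 169) versus week 26 (day 183). Both count as responses.
- NCPD with constant weight: 4,385/(60 × 218) = 0.335 versus 5,085/(60 × 218) = 0.389 mg/kg/day, or +16%.

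**4. Example: 80 kg, 0.75 mg/kg from week 3, 1.0 mg/kg from week 6, DC week 8, CR week 12**

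- 6.8.1: 840 + 1,260 + 1,120 + 1,120 + 840 + 560 + 350 + 280 + 315 + 710 = 7,395 mg; CRmin at week 29, day 204.
- Footnote: 840 + 1,260 + 1,120 + 3,360 + 840 + 560 + 350 + 280 + 315 + 430 = 9,355 mg; CRmin at week 33, day 232, after the day-218 limit.
- NCPD: 0.424 versus 0.536 mg/kg/day, or +27%.

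**5. Spread over assumed timings**

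The grid crossed the 11 weight columns of Table 3 with four escalated doses, two escalation speeds, DC at 1–3 weeks after the last escalation, and CR at 2, 4, 6 or 8 weeks after DC. Each dose has 264 combinations.

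- For 0.75–1.25 mg/kg, NCPD rises by 0.03–0.15 mg/kg/day (+9% to +38%).
- CRmin moves past day 218 in 0 of 264 combinations at 0.75 mg/kg, 68 at 1.0 and 39 at 1.25. All 68 at 1.0 mg/kg come from the slow escalation, one step every 3 weeks. These are counts of assumed scenarios, not participant rates.
- If EoC is met later, so that the trigger is DC + 8 weeks, 6 replaces 4 in both formulas.

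**The case against.** The best defence is that nobody can carry out a taper from the footnote alone. It gives no dose, step or interval. Those are in Table 3, which sits in Section 6.8.1, and Table 2 sends the reader to 6.8.1 for the prednisone dose. Section 8 describes the SoA as a summary of procedures and their timing. Four other places state the DC rule.

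Most of this stands. It makes 6.8.1 the governing text and the defect minor. It does not make the footnote right. Table 3 shows doses and tapering frequency but not when to start, and the footnote fills that gap wrongly, in four schedules and with no cross-reference.

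Three stronger readings are tempting, and the documents do not support them:

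- **That sites are caught between two binding instructions.** Section 8 does say "Adherence to the trial requirements, including those specified in the SoA, is essential and required for trial conduct", and 6.8.1 says "The investigator should not implement any deviation from the concomitant oral prednisone (or equivalent) regimen, except for immediate safety concerns of the participants". But the second sentence sits inside 6.8.1 and protects the regimen set out there, and the first follows directly on the description of the SoA as a summary. Both point to 6.8.1, so there is no deadlock.
- **That the footnote in particular breaches "Maximum escalation to 1.5 mg/kg qd for 3 weeks".** The footnote would lengthen the time at 1.5 mg/kg. But 6.8.1's own rule, with DC 2 or 3 weeks after reaching that dose and a further 2-week hold, already gives 4–5 weeks, in 176 of the 264 combinations. The next sentence of 6.8.1 speaks of a minimum of 3 weeks at that dose before treatment failure is declared, so a strict ceiling is doubtful. Correcting the footnote would not settle that question.
- **That the treatment comparison is biased.** The wording is the same for both blinded arms. The documents give no escalation rate by arm and no rate at which sites might follow the footnote, so no direction or size can be stated.

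**Conclusion.** The footnote is wrong as written for one group: participants who reach DC on more than 0.5 mg/kg. It is correct for everyone else and for all tapering below 0.5 mg/kg. This is an internal inconsistency of minor severity in an operative schedule. The design itself is fully stated in 6.8.1.

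The sizes in the working are illustrations. They rest on assumed DC and CR times, the earliest EoC trigger, no flare, and a site acting on the footnote instead of 6.8.1. After a single step to 0.75 mg/kg, no response was lost in the assumed scenarios. A lost response needs escalation to a higher dose. How often either condition would arise cannot be known from the documents.

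**What to change.** Amend the footnote in protocol Tables 1, 10, 16 and 18 to read:

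> For participants who reach DC on more than 0.5 mg/kg, tapering to 0.5 mg/kg begins 2 weeks after DC (Section 6.8.1); tapering below 0.5 mg/kg begins 2 weeks after CR or 4 weeks after sustained EoC.

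Notify sites of the correction. The copy in SAP 9.5 can follow at the next revision; that is optional and changes no result.

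The cost is one sentence in four footnotes and a site notice. No new data are needed and no analysis changes.

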2. INTRODUCTION

The proposed trial is a prospective, multicenter, randomized, double-blinded, placebo-controlled trial to investigate the efficacy, safety, tolerability, immunogenicity, pharmacokinetics (PK), and pharmacodynamics (PD) of efgartigimod PH20 SC in adult participants aged from 18 years with moderate to severe pemphigus vulgaris (PV) or pemphigus foliaceus (PF). This trial intends to demonstrate that efgartigimod PH20 SC with an add-on therapy of low doses of oral prednisone is a possible treatment modality for PV and PF, the administration of which will lead to early disease remission at minimal prednisone dose.

In order to allow for a convenient subcutaneous (SC) administration with efgartigimod to achieve the targeted exposure and PD effect, efgartigimod will be coformulated with recombinant human hyaluronidase PH20 (rHuPH20). This compound is being used in coformulations with approved therapeutic antibodies to facilitate SC administration with volumes >2 mL. The use of rHuPH20 in combination with other therapeutic proteins typically increases the absorption rate of these proteins, albeit to different extents. Increased rate of absorption of efgartigimod by rHuPH20 is expected to increase the overall exposure to efgartigimod after SC administration allowing administration of a SC dose in an acceptable volume and duration of administration that targets an exposure that results in a close to the maximal PD effect.

China- and Germany-specific modifications to the protocol are outlined in Section 10.16 .

